	
 ▪ Defined as median and rates of patients alive at pre-defined timepoints (12 and 18 months) after start of 1L therapy. ○ Proportion of different drug regimen in 1L 
 ▪ Defined as percentages of therapy protocols used as 1L therapy. ○ Best response rate (RR) in 1L 
 ▪ Defined as best response (complete response (CR) / partial response (PR) / stable disease (SD) / progressive disease (PD) / not done (ND)) recorded from the start of the therapy until disease progression/recurrence based on investigator's assessment. A confirmation of response is not required. ○ Duration of Response (DoR) in 1L 
 ▪ Defined as time from documentation of first disease response to disease progression. ○ Time to progression (TTP) in 1L 
 ▪ Defined as time from start of therapy until objective disease progression without including deaths. ○ Time to next treatment (TTNT) in 1L 
 ▪ Defined as time from last drug administered to initiation of next therapy. ○ Dose modifications and discontinuations in 1L 
 ▪ Defined of number of patients with at least 1 dose modification (reduction of dose or cancelling of administration) or with an interim/permanent discontinuation of one or all drugs of a therapy. ○ Handling after dose modification or discontinuations in 1L 
 ▪ Defined as continuation of therapies after dose modifications or temporary/permanent discontinuation of single drugs. 
The clinical outcomes will be analyzed for the total group of all patients and for following subgroups:
 
 ○ Age: < 70 years vs. ≥70 years ○ Gender: male vs. female ○ Risk rating: favorable (low) vs. intermediate vs poor (high) risk ○ Medical disciplines: urology vs. medical oncology ○ Institutions: practices vs. hospitals
Milestones	
Planned milestones:
 
 ● Start of data collection: 1 October 2022 ● Interim analysis (expected): 31 October 2022 ● End of data collection: 30 January 2023 ● Final study report: 15 April 2023

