8.1. Primary Research Questions

Based on the above background, there are currently a number of unanswered questions for health services research:

- How is the effectiveness, defined as measurement of beneficial effects under “real world” clinical settings, (e.g. progression-free survival, overall survival and best response) of TKI and/or ICI as 1L in patients with aRCC?
- How are patients with aRCC treated in 1L under daily care conditions in Germany in general and in accordance to medical specialities (urology and medical oncology) and treatment settings (hospitals vs office-based practices)?
- Are all patients assigned to individual risk ratings under standard daily care conditions according to a scale developed by the IMDC before start of a 1L?
- How are patients treated in 1L in different risk rating groups and how is the adherence to national/international guidelines?
- What kind of previous and subsequent therapies are administered before and after 1L?
- How often are evaluations for PD-L1 expression performed before start of 1L and how many patients are positive (TPS $\geq 1\%$) or negative?

- How long are patients treated with TKI + ICI and ICI + ICI in 1L in general and in relation to specific therapies like avelumab + axitinib?
- How frequent are dose modifications and early discontinuations and what are the reasons?
- Are there differences in the handling of modifications among medical disciplines?

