9.1.1. Inclusion criteria

Patients must meet all of the following inclusion criteria to be eligible for inclusion in the study:

Part 1 and 2:

- Patients aged ≥ 18 years old
- Patients with histologically/cytologically confirmed renal cell carcinoma (ICD-10 C64)
- Full medical information regarding all treatments before, during and after 1L should be available.

Specific inclusion criteria only for Part 1:

- Patients with locally advanced or metastatic disease and a start of any systemic 1L therapy against RCC between 01 January 2020 and 31 December 2021

Specific inclusion criteria only for Part 2:

- Patients with locally advanced or metastatic disease, who were treated with a combination of ICI + TKI or ICI + ICI as 1L therapy against RCC and who had a completion of this therapy between 01 January 2020 - 31 December 2021 with a follow-up period of at least 3 months after completion of the 1L.

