9.2. Variables

The following variables will be captured by a specific eCRF and are needed for the analysis of all outcomes and for answering all research questions.

Tab. 2: List of all variables, role, data source and operational definitions

Variable	Role	Data source(s)	Operational definition
Age and gender	baseline characteristic	Medical Chart	Years; male/female
Weight and body surface	baseline characteristic	Medical Chart	kg, m ²
Date of first diagnosis	baseline tumor characteristic	Medical Chart	dd/mm/yyyy
Stage and risk rating (IMDC) at first diagnosis and at start of 1L	baseline tumor characteristic	Medical Chart	Favorable risk / intermediate risk / poor risk
Assessments and results of PD-L1 expression as TPS	baseline tumor characteristic	Medical Chart	y/n; 0-100%
Non-medicinal pre-treatments (primary OP, cytoreductive nephrectomy radiotherapy)	baseline tumor characteristic	Medical Chart	y/n; dd/mm/yyyy of OP; mode of OP; intention of OP (curative/palliative); period and dose of radiotherapy
Medicinal pre-treatments (adjuvant, neoadjuvant)	baseline tumor characteristic	Medical Chart	y/n; start/stop and used therapy protocol
Location of administration and performing medical discipline	Relevant for outcomes	Medical Chart	Urological practice; hematological practice; hospital with urological department; hospital with oncological department
Administered drugs / protocols in 1L	Relevant for outcomes	Medical Chart	administered therapy protocol
If applicable: Reason for ineligibility of ICI	Relevant for outcomes	Medical Chart	Concomitant disease; patient's wish
Duration of 1L	Relevant for outcomes	Medical Chart	Start/stop of therapy or every cycle;

Dates of administrations for i.v. drugs in 1L	Relevant for outcomes	Medical Chart	Dates of every administration
Dosages per administration	Relevant for outcomes	Medical Chart	Dose of administered drugs per administration
Dose modifications or drug administration cancelling or interim/permanent discontinuations of single drugs / complete therapy in 1L	Relevant for outcomes	Medical Chart	Each for single/all drugs: Dose modification; cancelling single administration; temporare discontinuation; permanent discontinuation
Reasons for modifications, cancelling of single administrations and discontinuations in 1L	Relevant for outcomes	Medical Chart	Each for single/all drugs: intolerance; age; performance status; patient's decision; other

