Supportive drugs prescribed during 1L	Relevant for outcomes	Medical Chart	Administered supportive drugs in connection with cancer therapy
Date of first response and best response in 1L incl. date and mode of assessment	Relevant for outcomes	Medical Chart	dd/mm/yyyy; CT/MRI/ultrasound/x-ray; clinical assessment; laboratory
Assessment of first and best response in 1L	Relevant for outcomes	Medical Chart	CR/PR/SD/PD/ND
Date of tumor progression	Relevant for outcomes	Medical Chart	dd/mm/yyyy
Reasons for end of 1L	Relevant for outcomes	Medical Chart	Progression; intolerance; decision oncologist; patient's wish; death; deterioration performance
Subsequent therapies (Second-line therapy (2L) and higher) with drugs/protocol and dates for start / end	Relevant for outcomes	Medical Chart	y/n; used drugs/regime; start/stop
Concomitant diseases and therapeutic measures	Relevant for outcomes	Medical Chart	Detailed diagnosis; therapeutic measures OP/medicinal/none/other

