9.7. Quality control

The most relevant step in quality control and quality assurance will be an avoidance of inaccuracies or mismatches in terminology by data entries in data fields over a selection of parameters or descriptions out of pre-defined drop-down-lists. Free text is only intended for descriptions after selection of "other", which will be possible in some data fields, where a pre-definition cannot be

implemented for 100%. For all dates regarding parameters like first diagnosis, pre-treatments, therapy administrations automatic checks are implemented for data entries, so that the course of treatment will be shown correctly (e.g. adjuvant therapy after OP and before palliative therapy, end of 1L before start of 2L, end of therapy after last administration). In defined data fields new explanation fields will open up after selection of specific documentations (e.g. after selection of dose modification query for modified dose, after selection of end of therapy query for reason). In data fields with information like weight, height or age, automatic standard range checks, are implemented to avoid input errors. In addition to these automatic checks every data entry will also be checked by an experienced data manager and, if needed, by the medical lead.

In case of relevant inaccuracy or implausibility, patient's data files will be rejected before further analytical processes will start. After the decision for rejection of patients the investigator will be informed about the reason for rejection and all data will be deleted immediately.

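### The end-of-1L reason list has no value for a planned end and no 'other', so planned ends cannot be reliably separated from early discontinuations

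*Combined protocol and SAP*

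**What the plan says.** Section 8.1 asks: "How frequent are dose modifications and early discontinuations and what are the reasons". Section 8.2 makes the frequency of discontinuations and their reasons a secondary objective.

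Tab. 2 in Section 9.2 holds two separate reason fields:

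- **Reasons for end of 1L:** "Progression; intolerance; decision oncologist; patient's wish; death; deterioration performance".
- **Reasons for modifications, cancelled administrations and discontinuations:** "Each for single/all drugs: intolerance; age; performance status; patient's decision; other".

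The events behind the second field are typed as "Dose modification; cancelling single administration; temporare discontinuation; permanent discontinuation". No type distinguishes a planned stop from an early one.

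The outcome in the Abstract (Data Analysis) counts patients with at least one dose modification or an "interim/permanent discontinuation of one or all drugs of a therapy". It makes no exception for a planned stop.

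Part 2 admits patients treated with a combination "who had a completion of this therapy between 01 January 2020 - 31 December 2021" (Section 9.1.1). Neither *early* nor *completion* is defined.

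Section 9.7 gives, as an example of its automatic prompts, "after selection of end of therapy query for reason". It limits free text to what follows a choice of *other*, which only some fields offer. Section 9.3 states that, because of the anonymisation, data management cannot send queries. Section 9.6 leaves detailed methods to a SAP.

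**The concern.** Every Part 2 patient has, by eligibility, reached the end of 1L. That therapy ended therefore distinguishes nobody, and the recorded reason has to show whether the end was early. The protocol selects on completion but offers no reason value that corresponds to it.

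Two results depend on this. One is the distribution of reasons, where the code for the oncologist's decision and the drug-level *other* could each contain planned ends next to quite different reasons. The other is the frequency of early discontinuation, which the outcome definition does not separate from permanent discontinuation in general. A SAP written later can change how values are tabulated, but it cannot supply a value that was never collected.

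**Working it through.** The plan states no figure for planned ends, so the check is mainly a comparison of the fields, followed by a sensitivity calculation.

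**Step 1: a planned end of the whole therapy.** The site enters an end of therapy and is asked for a reason. The six values cover progression, intolerance, the oncologist's decision, the patient's wish, death and deteriorating performance. With no planned-end value and no *other*, the nearest is the oncologist's decision. That code also takes stops that the physician chose for other reasons, so the two become indistinguishable in this field.

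**Step 2: a planned end of one drug.** The drug-level list has five values: intolerance, age, performance status, the patient's decision and *other*. It has no value for physician decision. A planned stop can go only under *other*. Free text there would allow recovery if this field is one of those that offer it and if sites use it consistently. The protocol does not say that it is.

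**Step 3: the numerator.** The outcome includes any permanent discontinuation of one or all drugs. If a site records a planned stop as a permanent discontinuation, nothing in the definition removes it.

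**Step 4: what other data can recover.** Tab. 2 also captures the regimen, start and stop of therapy or of each cycle, the date of every i.v. administration, and doses. For i.v. drugs these show when treatment stopped and how many administrations were given. They do not record whether the stop was intended. Tab. 2 asks for administration dates only for i.v. drugs. Sites cannot be queried.

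**Step 5: sensitivity of the frequency.** Inputs:

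- p = 22%, the upper discontinuation figure that Section 8 cites for nivolumab + ipilimumab, used only as an illustrative rate of unplanned discontinuation;
- n = 300, the planned size of Part 2 (Section 9.4);
- s, the share of the remaining 78% with a planned stop that is counted as a discontinuation. This is an assumption; the documents give no value.

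Observed rate = 22 + 78 × s (in %):

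| s | Calculation | Observed rate |
|---|---|---|
| 0% | 22 + 0 | 22.0% |
| 5% | 22 + 3.9 | 25.9% |
| 10% | 22 + 7.8 | 29.8% |
| 20% | 22 + 15.6 | 37.6% |

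Sampling error for comparison: the 95% half-width is 1.96 × √(0.22 × 0.78 / 300) = 0.047, or 4.7 points. The shift 78 × s exceeds this once s is above 4.7 / 78 = about 6%. A single-regimen subgroup is smaller than 300 and has a wider interval, so the threshold there is higher.

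**The case against.** The strongest objections, and what stands of each:

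- **The drug-level list is not closed.** Correct. It contains *other* and has no physician-decision value. A reader might infer that planned ends at every level are recorded as physician decision. The documents support that only for the end-of-1L field, and there only as the most likely choice.
- **No passage says planned ends are counted as early discontinuations.** Also correct. Tab. 2 keeps the end of 1L separate from discontinuations, and a SAP is still to come. The outcome definition permits the mixing but does not prescribe it. What stands is that the recorded values do not allow a reliable separation afterwards.
- **Toxicity data are unaffected.** Largely right. Intolerance is a value in both lists, so those stops stay identifiable. Most of the trial discontinuation figures in Section 8 are described as led by adverse events, and the intolerance code is their natural comparator. Section 7 places its particular emphasis on handling of intolerabilities, which this gap touches less than it touches the overall reason distribution.
- **I.v. dates and regimen allow reconstruction.** In part, as Step 4 shows.
- **No regimen with a planned end is named.** True. The documents describe palliative systemic therapy, and how often planned ends occur cannot be derived from them. It could be close to zero.
- **A distorted comparison of ICI + TKI with ICI + ICI.** A reader might infer this, but no comparison of discontinuation frequency between these groups is stated. The listed subgroups are age, gender, risk, discipline and institution.

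**Conclusion.** The gap is real and limited. The end-of-1L list cannot record a planned end, the drug-level list can hold one only within a residual category, and the outcome does not separate early from planned permanent stops. As queries are excluded, the loss is only partly recoverable after data collection.

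The size is unknown. The figures in Step 5 restate an assumed share and are not an estimate of bias; at s = 0 there is none. They show only that a share above about 6% would outweigh the sampling error in 300 patients, if 22% were the true unplanned rate and all planned stops were counted.

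The conclusion assumes that the eCRF offers the values listed in Tab. 2 and no others. The primary outcome (PFS) and the sample size do not depend on this point. It merits correction because it affects a stated secondary objective and costs very little before data collection.

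**What to change.** Before data collection starts (planned for 1 October 2022):

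1. Add a planned or regular end as a value in both reason lists of Tab. 2, and add *other* with free text to the end-of-1L list.
2. In the discontinuation outcome, tabulate permanent discontinuations by reason, with planned end, progression and death shown separately.
3. Count as early discontinuation only permanent stops of one or all drugs for reasons other than planned end, progression or death. Excluding planned ends alone would not be enough: all Part 2 patients have ended 1L, so nearly everyone without a planned end would be counted as an early stop.
4. Define *completion* in the Part 2 criterion. Progression and death appear only in the end-of-1L list, so the SAP should also say that this field supplies the reason when the whole therapy stops.

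The cost is three drop-down entries, a few sentences of definition and one more table. This changes data coding only and sets no clinical rule.

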9.3. Data sources

Source documents (paper or electronic medical charts) are those, in which patient data of daily care are recorded and documented in individual patient files. The data to be collected in the study will be obtained via a specific programmed eCRF. The data in the eCRF should be consistent with the relevant source documents. Medical records should contain demographic data, medical data, treatments and diagnostic documentations according to common practice. The documentation will be performed under full anonymization, so that a re-identification of single patients will not be possible. Based on this anonymization, queries for explanations or changes of data could not be submitted by the data

management. All documented variables will be checked by data manager and/or medical lead of GermanOncology in relation to implausibility, inaccuracies or missing data. If implausibility or inaccuracies or missing data of single patients will be of great relevance for analyses, the data management and/or medical lead have the right to reject patients. For such rejected patients no payment will be triggered.

9.4. Study size

Based on public data the population of patients with aRCC and an indication for a 1L therapy is around $n = 4.500 - 5.000$ patients per year ([Robert Koch Institute 2020](#)). In the period of 01 January 2020 – 31 December 2021, which is the main period of interest in the study for completing or starting 1L therapies, the total population of patients with aRCC would be around $n = 9.000 - 10.000$ patients. To estimate the needed number of patients in the study to reach adequate representation across Germany, the following common formula is used

$$n = \frac{z^2 \pi(1 - \pi)N}{z^2 \pi(1 - \pi) + E^2(N - 1)}$$

N = population of patients with aRCC and indication for 1L = 10.000 patients in 24 months

$\Pi = 0,5$ (consensus, if attribute is unknown before study)

E = margin of error = 5% = 0,05

$Z = 1,96$ (for confidence interval of 95%)

Based on these assumptions (PFS of 1L therapies included in guidelines was 8.4 – 151 months in clinical studies) the number of patients needed for representative statement regarding the primary objective (= PFS rates at defined time points under real world conditions) is at least $n = 370$. With a buffer of around 10% the sample size in the study should be $n = 400$ patients with aRCC and 1L therapies in the period from 01 January 2020 – 31 December 2021. Based on published data for PFS it could be assumed for part 2, that also the number of patients with combination therapies in part 2 ($n = 300$) will grant a representative statement to all research questions. Based on information of urological and oncological experts as well as own data of the GermanOncology *¹ network (see below), the following assumptions could be set:

- Number of patients with new 1L in urological practices (per practice 1- 3 urologists) = 4 - 6 per year
 - Number of patients with new 1L in period of 24 months = 8 - 12
- Number of patients with new 1L in oncological practices (per practice 2- 4 oncologists) = 4 - 6 per year
 - Number of patients with new 1L in period of 24 months = 8 - 12
- Number of patients with new 1L in hospitals with urological focus = 8 - 12 per year
 - Number of patients with new 1L in period of 24 months = 16 – 24
- Proportion of 1L therapies in urological and oncological practices: 50% : 50%
- Proportion of patients treated with 1L in practices and hospitals (as most of therapies are oral therapies): 65% : 35%

Based on the assumptions the needed number of sites are at least:

- Number of urological practices: 15
- Number of oncological practices: 15
- Number of hospitals with urological focus: 10
- Total number of sites across Germany: 40

9.5. Data management

The main purpose of the specific eCRF is to obtain data required by the study protocol in a complete, accurate, legible and timely manner. The data in the eCRF should be consistent with the relevant source documents in the practices and hospitals. The investigator or his/her designee is responsible for ensuring that the data collected in the course of this study are accurate and documented appropriately and completely in all applicable forms. Data will be documented, processed, evaluated, and stored in fully anonymous form in accordance with applicable data protection regulations. The investigator must ensure that the eCRFs and any other associated documents forwarded to the project management contain no mention of any subject names or other personalized information. The data will be entered by the eCRF into a validated database. The project management will be responsible for data processing, in accordance with the Sponsor's data management procedures. The sponsor will receive only full anonymized data or aggregated reports, without any options for re-identification of patients and/or sites. Database lock will occur once quality control and quality assurance procedures and second, that activities of documentation and coding have been completed. The eCRF has a modular structure with separation of contents to build up all sequences and information of treatments from date of first diagnosis up to the present date or death or lost-of-follow-up. Data must be filled in completely and legibly by choosing parameters out of a pre-defined drop-down-list, or in a few cases by writing free text. All corrections will be listed in a history trail with name of corrector and date of correction. Relevant fields are declared as mandatory and must be fulfilled definitively before triggering any payment. As part of the data quality process, all entries in the eCRF will be checked by data manager. In cases of implausibility or incorrectness or inaccuracy or relevant missing data, the data manager together with the medical lead of GermanOncology are allowed to reject patients with a statement of an appropriate reason. Every patient's documentation file is given a randomized code of numbers and letters, automatically generated by an encryption algorithm. As only anonymized data will be sampled, this data handling and storage can be described as "full anonymized" in accordance to the recital 25 of the German and EU General data protection regulation.

